9.2 Assessment of immune response

Bone marrow research samples obtained (only for those who consent for screening research sample consents) will be analyzed to determine the presence of common multiple myeloma tumor associated antigens (TAAs) including survivin, WT-1, NY-ESO, and MAGE using immunohistochemistry (IHC) or polymerase chain reaction (PCR). Prior biopsy specimens may be requested if available, in order to perform IHC for the described TAAs. Research blood samples will be obtained prior to transplant, at baseline (prior to the initiation of maintenance), after 3 cycles of maintenance therapy, and after panobinostat maintenance

(after completing of therapy) to evaluate for the presence of T-cell precursors against individual patient's identified TAA using peptide pools.

As a standard of care, all autologous HCT recipients will receive heptavalent pneumococcal conjugate vaccine (PCV13, Prevnar™) at around 3 months from the time of transplant. We hypothesize that patients immunized with heptavalent pneumococcal conjugate vaccine, who then receive panobinostat maintenance therapy, may have augmented immune responses. (stan Each vaccine specific serotype IgG level will serve as a marker for immune response. We propose to measure following anti-pneumococcal IgG antibody serotype panel at baseline, at cycle #6 and after completion of maintenance (completion of 12 cycles) to assess immune reconstitution with panobinostat maintenance therapy. The antibody panel contains serotypes 1, 4, 5, 7F, 8, 9V, 9N, 12F and 18C. A positive response of IgG antibody is considered to be greater than or equal to 1 microgram/mL. Patients may also receive standard of care pneumococcal conjugate vaccine (usually at 6 months and 12 months after autologous HCT).

T cell response in the setting of panobinostat maintenance therapy will be evaluated at baseline, after cycle #3 and cycle #6, and after completion of maintenance therapy (completion of 12 cycles). Specifically we will measure the % of T1 cells and cytotoxic T cells specific for intracellular IFN-gamma production after co-culture of patients with T cells with the inactivated diphtheria conjugate (CRM197) which is a component of the pneumococcal conjugate vaccine.

In addition, we will evaluate the phenotype of T cells at baseline, after cycle #3 and #6, and after completion of maintenance therapy (completion of 12 cycles). We will employ flow cytometry panels. In brief, whole PBMCs will be stained with flow cytometry antibodies for CD3, CD4, CD8, CD62L, CD45RO, and CD95 in order to evaluate for naïve, effector memory, or central memory phenotype. We will also test for CD4, CD8, PD-1, PD-L1, CLTA-4, CD25, CD127, and FOXP3 to evaluate for costimulatory molecules and regulatory T cells.

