In our preliminary study (unpublished) with limited sample size, we compared two different bone marrow samples (CD138 selected DNA extract vs. formalin-fixed paraffin embedded (FFPE) bone marrow clot section) from same patients (from Moffitt Cancer Center) and demonstrated that high-throughput sequencing technology by Adaptive Biotechnologies can identify the index myeloma clones (data not shown). We hypothesize that high-throughput sequencing technology using PCR on CDR3 sequences will identify minimal residual disease in myeloma patients after autologous HCT followed by panobinostat maintenance and bone marrow samples will be obtained prospectively to analyze this technology.

3 Study rationale/purpose

Optimal maintenance therapy after autologous HCT in multiple myeloma has not been defined. Based on preclinical and clinical data demonstrating anti-myeloma activity of panobinostat, we propose an open-label, trial to determine the safety and tolerability of 2 dosing schedules of panobinostat maintenance therapy in patients with multiple myeloma who underwent autologous HCT. As noted in prior maintenance therapy in myeloma, the dose of maintenance single agent is usually started at a lower dose (such as 10 mg starting dose for lenalidomide maintenance compared to 25 mg full dose in relapsed/refractory disease treatment) due primarily to (1) lower disease burden after autologous HCT and (2) limited tolerability and susceptibility to cytopenias immediately after autologous HCT. Panobinostat maintenance therapy will be initiated between 90 days and 180 days after autologous HCT at a starting dose of (a) 20 mg PO three times a week, every other week, every 4 weeks (Cohort A), or (b) 10 mg po daily x 7 days, every other week, every 4 weeks (Cohort B). Maintenance therapy will be prescribed for a maximum for 12 cycles (4 weeks x 12 cycles = 48 weeks) for both cohorts. The dose delivered to each cohort would be 60 mg per week for Cohort A and 70 mg per week for Cohort B. Long-term tolerability of each dose schedule of panobinostat

maintenance therapy after autologous HCT is unknown and the study intends to evaluate the safety and tolerability in multiple myeloma patients.

4 Study objectives

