4.2 Secondary

- To evaluate the complete response rate to panobinostat maintenance therapy after autologous HCT.
- To determine the 2-year PFS and OS of autologous HCT followed by panobinostat maintenance therapy in patients with multiple myeloma.
- **Exploratory secondary objectives:**
 - To evaluate histone acetylation (H3 and/or H4) of peripheral blood mononuclear cells
 - To isolate and identify clonotypic B cell progenitors in multiple myeloma patients from the bone marrow, peripheral blood and stem cell grafts.
 - To evaluate T-cell immune response against known myeloma tumor associated antigens while on panobinostat maintenance.
 - To evaluate humoral immunity against pneumococcal serotypes included in the standard of care heptavalent pneumococcal conjugate vaccine, and to assess cellular immune responses against CRM adjuvant found in the heptavalent pneumococcal conjugate vaccine.
 - To evaluate minimal residual disease (MRD) after autologous HCT followed by panobinostat maintenance therapy using flow cytometry
 - To evaluate MRD after autologous HCT followed by panobinostat maintenance therapy using multiplex PCR for CDR3 sequences

5 Overall study design

This is an open-label trial to determine the safety and tolerability of 2 different dosing schedules of single agent panobinostat maintenance therapy in patients with multiple myeloma who underwent high-dose melphalan followed by autologous HCT in patients with multiple myeloma. It is unknown whether the toxicity profile of panobinostat will be accentuated in patients after autologous HCT in the setting of maintenance therapy, hence the dose chosen for maintenance therapy is lower than MTD dosing or other phase 2 studies. There are 2 dosing schedules evaluated in this protocol in order to assess optimal tolerable schedule for panobinostat maintenance therapy after autologous HCT. As secondary

objectives, we will evaluate response after completion of treatment, and 2-year PFS and OS. As correlative studies, we plan to evaluate MRD, and to assess clonotypic B cells following an autologous HCT. We also plan to evaluate T effector immune response after autologous HCT while on panobinostat maintenance therapy.

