6.1.3 Inclusion and exclusion criteria (for panobinostat maintenance)

Patients will be enrolled to the panobinostat maintenance therapy study after receiving autologous HCT. Patients must have baseline evaluations performed prior to the first dose of study drug and must meet all inclusion and exclusion criteria. Results of all baseline evaluations confirming eligibility must be reviewed by the Principal Investigator (or co-investigator) prior to enrollment of that patient. In addition, the patient must be thoroughly informed about all aspects of the study, including the study visit schedule and required evaluations and all regulatory requirements for informed consent. The written informed consent must be obtained from the patient prior to enrollment. The following criteria apply to all patients enrolled onto the study unless otherwise specified.

Inclusion criteria (for panobinostat maintenance)

1. Adult patients, age ≥ 18 years old
2. Ability to provide written informed consent obtained prior to participation in the study and any related procedures being performed
3. Histologically confirmed diagnosis of multiple myeloma
4. Meeting the criteria for symptomatic multiple myeloma (“CRAB” criteria – See **Appendix B**) before the initiation of systemic chemotherapy
5. Received high-dose melphalan (≥ 140 mg/m²) followed by autologous HCT based on the institutional guidelines and within +45 and +180 after autologous HCT at the time of panobinostat maintenance initiation.
6. Patients must have achieved at least PR prior to autologous HCT and must not have progressive disease (PD) prior to the initiation of maintenance therapy (See **Appendix C** for response criteria)
7. Patients must meet the following laboratory criteria (prior to the initiation of panobinostat maintenance):
 - ANC $\geq 1 \times 10^9$ /L
 - Hemoglobin ≥ 8 g/dl
 - Platelets $\geq 50 \times 10^9$ /L (without transfusion support)
 - Creatinine clearance ≥ 40 ml/min or serum creatinine $\leq 2.5 \times$ ULN
 - AST and ALT $\leq 2.5 \times$ ULN
 - Serum bilirubin $\leq 1.5 \times$ ULN
 - Albumin > 3.0 g/dl
 - Clinically euthyroid. Note: Patients are permitted to receive thyroid hormone supplements to treat underlying hypothyroidism.

8. Baseline (pre-HCT) MUGA or ECHO must demonstrate LVEF \geq the LLN of the institutional normal.
9. ECOG Performance Status of ≤ 2 or Karnofsky performance status $\geq 70\%$ (See **Appendix D** and **Appendix E**)

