7.1 Investigational therapy

[figure not shown]
Screening consents will be signed prior to autologous HCT to access pre-HCT stem cell graft, bone marrow and peripheral blood samples for the correlative studies. Patients will be enrolled after autologous HCT. Patients will be initiated on panobinostat maintenance therapy between day +90 and +180 after autologous HCT. Patients who develop disease progression before day +90 after autologous HCT will be ineligible for the study.

Panobinostat (also known as LBH589) will be provided by Novartis. Oral panobinostat will be supplied as 5-mg, 10-mg, 15-mg or 20-mg pink/opaque-colored, hard gelatin capsules.

Medication labels will comply with US legal requirements and be printed in English. They will supply no information about the patient. The storage conditions for study drug will be described on the medication label.

During the study, panobinostat will be administered orally as either (1) once daily dose of 20 mg (1 x 20-mg capsule) three times per week, every other week, of a 28-day schedule (Cohort A), or (2) once daily dose of 10 mg (1 x 10-mg capsule) daily x 7 days, every other week, of a 28-day schedule (Cohort B). Both cohorts will receive a maximum of 12 cycles of maintenance therapy (Figure 7-1).

Figure 7-1. Panobinostat maintenance schedule

Patients should be instructed to take their once-a-day oral dose of panobinostat at the same time each morning. Each dose of panobinostat should be taken with an 8 oz / 240 ml glass of water. Patients should be instructed to swallow the capsules whole and not chew them. Patients must avoid grapefruit or grapefruit juice and seville (sour) oranges during the entire study.

If a subject experiences toxicity, the dose of panobinostat will be reduced to one level lower (Table 7-1) and maintained at this level for all subsequent cycles unless further toxicities occur. Panobinostat dose modifications will be made according to the toxicity grading. Once a subject's dose of panobinostat is reduced, then that dose will be the maximal dose administered.

On the days of ECG monitoring, drug administration should be supervised by study center personnel and administration time should be recorded.

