7.5.4 Pneumococcal-13 conjugate vaccine administration (standard of care)

As a standard of care, pneumococcal-13 conjugate vaccine (Prevnar-13™) will be administered to many of autologous HCT recipients at around day +90 (prior to the initiation of maintenance therapy).

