8.1 Visit schedule

Table 8-1 Evaluation and visit schedule

	Pre-HCT (Screening, not required)	Prior to maintenance (Enrollment: +45 to +180) [§]	Cycle #1 (start between +90 and +180)	Cycle #2****	Cycle #3****	Cycle #4****	Cycle #5****	Cycle #6****	Cycle #7****	Cycle #8****	Cycle #9****	Cycle #10*** *	Cycle #11*** *	Cycle #12*** *	End of study visit (4 weeks (± 14 days) follow up after the first dose of cycle #12)
Consent	X ⁺	X													
Enrollment		X													
H&P (SOC)		X	X ^{SS§}	X	X	X	X	X	X	X	X	X	X	X	X
Concomitant medications		X													
Toxicity (adverse event (AE)) assessment ^{SS}			X	X	X	X	X	X	X	X	X	X	X	X	X
Vital signs (SOC)		X ⁺⁺	X	X	X	X	X	X	X	X	X	X	X	X	X
EKG		X	X [*]	X ^{**}	X ^{**}	X ^{**}									
CBC and CMP (SOC)		X	X ^{***}	X ^{***}	X	X	X	X	X	X	X	X	X	X	X
PT/INR/PTT		X			X			X							X
LDH, cholesterol panel, GGT, uric acid		X													
Urinalysis		X													X
TSH, free T4		X													X
Serum pregnancy test ⁺⁺⁺		X	X	X	X	X	X	X	X	X	X	X	X	X	
SPEP, UPEP and serum free		X			X			X			X			X	

Confidential

light chains (SOC)															
Pneumococcal-13 conjugate vaccine (at around day +90 – SOC)		X [#]													
Peripheral blood research samples	X	X	X ^{****}	X	X			X			X				X
Bone marrow research samples	X [@]	X													X
Stem cell graft research samples	X														

*Single 12 lead EKG will be performed for pre-dose and 3 hours (± 15 minutes) post-dose on days 1 and 5 of cycle 1. A total of 4 EKGs during cycle 1 will be performed.
 **Single 12 lead EKG will be performed for pre-dose on day 1 of cycle 2 and beyond at each cycle (at least through cycle 4). If no significant QTcF prolongation is noted during the first cycle, then QTc monitoring is no longer required beyond cycle 4 (and may be performed at the investigator’s discretion). One EKG per cycle from cycle 2 to 4 (minimum).
 ***CBC to be performed weekly during cycle #1 and #2. CBC/CMP will also be performed on day 5 of cycle 1.
 ****Window to start cycles #2 to #12 would be ±7 days from the planned first day of each cycle.
 + Screening consent for research samples (bone marrow, peripheral blood and stem cell graft)
 ++ Height will be measured at screening visit prior to starting panobinostat maintenance therapy
 +++ Only for women of child bearing potential
 ++++ Peripheral blood research samples will be also collected on day 5 of cycle 1.

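### Both post-baseline pneumococcal IgG titres fall after the usual month-6 re-vaccination date, later doses are not recorded and response is an absolute level, so a rise cannot be traced to its source

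*Combined protocol and SAP*

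**What the plan says.** Section 9.2 hypothesizes that patients vaccinated around three months after transplant and then given panobinostat may have a stronger immune response. IgG by serotype is measured at baseline, at cycle 6 and after 12 cycles. A positive response is a level of at least 1 microgram/mL. The serotype levels are also named as the marker, but no rule for change is given. Later doses are foreseen: "Patients may also receive standard of care pneumococcal conjugate vaccine (usually at 6 months and 12 months after autologous HCT". On the assay: "The antibody panel contains serotypes 1, 4, 5, 7F, 8, 9V, 9N, 12F and 18C". The objective in Section 4.2 reads: "To evaluate humoral immunity against pneumococcal serotypes included in the standard of care heptavalent pneumococcal conjugate vaccine".

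On timing, Section 7.1 states: "Patients will be initiated on panobinostat maintenance therapy between day +90 and +180 after autologous HCT". Inclusion criterion 5 in Section 6.1.3 instead has "within +45 and +180 after autologous HCT at the time of panobinostat maintenance initiation". Section 3 gives the treatment length as "4 weeks x 12 cycles = 48 weeks". In Table 8-1, the baseline research blood and the vaccine share one column, "Prior to maintenance (Enrollment: +45 to +180", with no order between them.

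Section 9.2 says all transplant recipients are vaccinated, whereas Section 7.5.4 says the vaccine "will be administered to many of autologous HCT recipients at around day +90". Table 8-1 schedules no later vaccine dose, and Section 7.5 collects other concomitant medications once, at enrollment.

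**The concern.** The IgG results are meant to say something about vaccine response under panobinostat. A further dose of conjugate vaccine is an obvious competing cause of a higher titre, and both post-baseline samples come after the date when one is usually given. Because those doses are optional and not recorded, the analyst would face an unknown mix of boosted and unboosted patients, with no means of adjusting for it or excluding anyone.

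Two further features add to this. If the baseline precedes the day +90 dose, the rise to cycle 6 includes the first vaccine response; if it follows, some or all of that response is already in the baseline. And an absolute cut-off counts as a responder anyone who was above it before treatment. Section 13.1.4 then relates immune response to clinical response, PFS and OS in Cox models, so the same ambiguity carries into those analyses.

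**Working it through.** **Inputs.** Start day S is +90 to +180 (Sections 3 and 7.1, Table 8-1), with +45 as a sensitivity bound (Section 6.1.3). Cycles last 28 days. Table 8-1 allows ±7 days for cycles 2 to 12 and ±14 days for end of study. Section 8.3 has patients seen on day 1 of each cycle, so the cycle 6 titre is taken as cycle 6 day 1; a draw later in the cycle would only move it further past month 6. Month 6 is taken as day 180 to 183 and month 12 as day 360 to 365 (assumption).

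**The plan's own figure.** 12 × 28 = 336 days = 48 weeks, as Section 3 states.

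**Sample dates.** Cycle k day 1 = S + 28(k − 1). End of study = S + 28 × 11 + 28 = S + 336.

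| Sample | Offset | S = +90 | S = +180 | Range with window | IgG planned in 9.2 |
|---|---|---|---|---|---|
| Cycle 2 day 1 | 28 | 118 | 208 | 111 to 215 | no |
| Cycle 3 day 1 | 56 | 146 | 236 | 139 to 243 | no |
| Cycle 6 day 1 | 140 | 230 | 320 | 223 to 327 | yes |
| End of study | 336 | 426 | 516 | 412 to 530 | yes |

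Cycle 6 falls 230 − 180 = 50 to 320 − 180 = 140 days after day 180, and always before month 12. End of study falls 426 − 365 = 61 to 516 − 365 = 151 days after day 365.

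**Sensitivity to the start bound.** With S = +45, cycle 6 is day 45 + 140 = 185, or 178 at the early edge of its window, so it can just precede month 6. End of study is day 45 + 336 = 381, or 367 at the early edge, still after month 12.

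**Baseline.** Enrollment from +45 to +180 straddles day +90, so a baseline may be drawn before or after the first dose.

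**Responder rule.** As an illustration, suppose 20% to 80% of the 30 patients already have at least 1 microgram/mL for a given serotype at baseline (assumption). Then between 30 × 0.8 = 24 and 30 × 0.2 = 6 patients could newly reach the cut-off. The rest count as responders without any change, so long as their level holds.

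**Could an earlier sample be used?** Table 9-1 already draws blood at cycles 1, 2 and 3. If starts are spread evenly over the 91 days from +90 to +180 (assumption), cycle 2 day 1 is no later than day 180 when S ≤ 152, which is 63/91 = 69%. Cycle 3 day 1 is no later than day 180 when S ≤ 124, which is 35/91 = 38%. With month 6 at day 182.6 the shares are 65/91 = 71% and 37/91 = 41%. At cycle 6 the share is 0%.

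**Panel count.** Nine serotypes exceed a 7-valent product by at least 9 − 7 = 2. By count alone, all nine could lie within a 13-valent product, leaving at least 13 − 9 = 4 of its serotypes unmeasured.

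**The case against.** Several stronger readings are tempting, and the documents do not support them.

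- *Every later titre follows a booster.* Section 9.2 says patients may receive further doses, usually at 6 and 12 months. The titres follow the usual dates, not an actual re-vaccination in each patient. Cycle 6 precedes month 12, and a day +45 start can put it just before month 6.
- *The whole immune endpoint fails on timing.* The T-cell response to CRM197 is already tested after cycle 3. Read as S + 84, that is day +174 to +264, which precedes day 180 for starts up to +96. The timing defect concerns IgG.
- *The panel cannot match the vaccine.* The product is called heptavalent in Sections 2.2.4, 4.2 and 9.2 and in a Table 8-1 footnote. Yet Sections 2.2.4 and 9.2 also name PCV13, and Section 7.5.4 and the Table 8-1 row name a 13-valent product. This is a naming conflict. The documents do not list the vaccine's serotypes, so the real overlap cannot be judged.
- *Change cannot be analysed.* It can, because levels are the named marker and a baseline is drawn. What is missing is a pre-specified rule.

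The best remaining defence is that the objective is exploratory, that Section 9.2 describes the titres as assessing immune reconstitution, and that Section 12.1 allows data items to be added later, so vaccine dates might yet be collected. The first two limit the weight of the point; the third is a possibility, not a plan. It is also true that Section 7.2 provides no randomization and every patient receives panobinostat. Without a panobinostat-free control, no choice of sampling times could prove augmentation. That stands, and it limits what the fix can claim.

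**Conclusion.** The point holds for IgG. For starts at day +90 to +180, neither post-baseline titre precedes the usual month-6 re-vaccination date, and the last also follows month 12. With later doses unrecorded, a baseline of uncertain position and an absolute responder rule, a rise or responder rate during maintenance cannot be separated from a booster, the first vaccine response or pre-existing antibody.

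This rests on months 6 and 12 falling near days 180 to 183 and 360 to 365, and on patients reaching the visits on schedule. How many patients would be boosted is unknown. The result is a cheap, worthwhile improvement to an exploratory objective; the primary endpoint is not touched. A reader might infer that moving the samples would let the trial show that panobinostat augments vaccine response. It would not: it removes an avoidable confounder, and attribution would still need a control.

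**What to change.** 1. Record the date and product of every pneumococcal vaccine dose through end of study.
2. Run the IgG panel on blood already in Table 9-1: cycle 1 day 1, specified as pre-dose, as a common pre-panobinostat baseline, and cycle 2 or 3. Make the main IgG analysis the change from that baseline to the last sample before any re-vaccination, in vaccinated patients, and report the interval since vaccination.
3. Define response as a fold-rise from that baseline. Report the proportion at or above 1 microgram/mL at each time point as a level only.
4. Report cycle 6 and end-of-study titres by re-vaccination status. Describe all titres as immune reconstitution during panobinostat, not as augmentation by it.
5. Reconcile heptavalent with PCV13/Prevnar-13, *all* with *many* recipients, and the +45 with the +90 start bound. The last matters here because a start at +45 would precede the day +90 vaccine. Summarise separately any panel serotypes that are not in the product given.

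The cost is wording, a vaccine-date field and one or two extra antibody panels per patient on blood already drawn. The pre-booster set is smaller than the full cohort: with even start days, about 0.69 × 30 ≈ 21 patients at cycle 2 or 0.38 × 30 ≈ 12 at cycle 3, before any loss from unvaccinated or early-stopping patients.
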